## 3.6 Safety Endpoints

Safety profile will be characterized by type, frequency, and severity of adverse events, coded using the MedDRA coding system, as graded by NCI Common Toxicity Criteria for Adverse Events version 4.0 (NCI CTCAEv.4), timing and relationship to treatment, laboratory abnormalities, vital signs, and left ventricular imaging data.

## **3.6.1** Treatment-Emergent Adverse Events (TEAE)

Adverse events will be considered treatment-emergent if:

- The event occurs for the first time after the start of study treatment and on or before 30 days after final dose of study treatment and was not observed prior to start of treatment
- The event was observed prior to the start of treatment but increased in NCI CTCAE v4 grade during study treatment

The eCRF will capture TEAEs on the adverse event page, while those events occurring pre-treatment will be captured on medical history.

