### 9.2. Assessing and Documenting Adverse Events and Hospitalizations

Adverse event assessment will begin in conjunction with informed consent. Investigators should complete all routine and standard of care assessments to evaluate for toxicity and symptoms of drug-induced adverse events. This may include, but is not limited to, verbal reports from the patient and/or caregiver, physical examination and laboratory findings.

For all patients between informed consent and eligibility determination and for heregulin positive patients during their time on study, all adverse events, whether serious or not, will be described in the source documents and the adverse event page of the case report form. All new events, as well as those that worsen in intensity or frequency relative to baseline, which occur after first administration of study drug through the first Overall Survival follow-up visit or phone call, must be reported. However, new adverse events felt by the investigator to be related to study treatment, must be reported any time the investigator becomes aware of such an event, even if this occurrence is after the first Overall Survival follow-up. All adverse events should be followed until resolution, or until the patient discontinues from the overall survival follow-up portion of the study.

Laboratory, vital signs or ECG abnormalities are to be recorded as Adverse Events only if they are medically relevant: symptomatic, requiring corrective treatment, leading to discontinuation and/or fulfilling a seriousness criterion.

Information to be reported in the description of each adverse event includes:

- A medical diagnosis of the event (if a medical diagnosis cannot be determined, a description of each sign or symptom characterizing the event should be recorded)
- The date of onset of the event
- The date of resolution of the event
- A determination of whether the event is serious or not
- A determination of relatedness to the study drug
- Action taken with study drug: none; change in the study drug administration (e.g., temporary interruption in dosing); drug treatment required; non-drug treatment required; diagnostic or concomitant procedure performed; patient discontinued from the study (complete Treatment Termination case report form)
- Outcome: resolved without sequelae; resolved with sequelae; event ongoing; subject died (notify the Sponsor immediately, and complete the Serious Adverse Event page and the Subject Death page)

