#### 10. Statistical Methods

Detailed methodology for summary and statistical analyses of the data collected in this study will be documented in a Statistical Analysis Plan (SAP), which will be dated and completed prior to database lock. The SAP may modify the plans outlined in the protocol; however, any major modifications of the primary endpoint and/or its analysis will also be reflected in a protocol amendment.

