#### 10.5.4. Safety Analyses

Safety analyses (adverse events and laboratory analyses) will be performed using the safety population. Adverse events will be coded using the latest MedDRA dictionary. Severity of adverse events will be graded according to the NCI CTCAE version 4.03.

Treatment-emergent adverse events (TEAEs) are defined as any event that occurred after the first dose of study drug and was not present prior to study drug administration or worsened in severity after study drug administration. TEAEs will be collected through the end of treatment visit. Frequency and percent summaries will be presented for treatment-emergent adverse events (TEAE) defined as adverse events that occur or worsen in severity following the first dose of seribantumab, or fulvestrant. Additional tabulations include serious adverse events (SAE), TEAE-related to seribantumab, fulvestrant and TEAE grade  $\geq 3$ , and discontinuation due to TEAE. Adverse events will be summarized by System Organ Class and preferred term. All adverse event data will be listed by patient.

Maximum and minimum decrease in continuous laboratory data will be reported. Bar graphs depicting treatment arms will be reported. Frequency and percent of abnormal laboratory values (L/ULN, 2\*L/ULN) will be assessed. Shift to most severe toxicity grade will be summarized.

Vital signs, ECG, and ECHO/MUGA will be tabulated for the change from baseline by time point. Additional analyses may be performed as described in detail within the SAP.

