#### 5.6.2 Adverse Events

Adverse events will be coded using the latest MedDRA dictionary at the time of coding. NCI CTCAE v4.0 will be used to grade severity. Frequencies and percentages will be reported by System Organ Class (SOC) and preferred term (PT). Patients with multiple events for a category will be counted once in the highest CTCAE classification. Summary tables will include treatment-emergent AEs, unless specified otherwise. Treatment-emergent adverse events (TEAEs) will be defined as patients based on the event onset date relative to first dose of study drug in the study. Missing onset date for an event will be considered as TEAE. Adverse events with a starting date 30 or more days after the last dose date are not considered TEAEs. Relatedness will be considered: Possibly, Probably, or Definitely related per case report form classification. If relatedness is missing the adverse event will be considered TEAE. The order of reporting the events in summary tables will be according to the following where applicable:

- SOC will be alphabetically reported
- Descending order of frequencies according to the number of patients in the seribantumab treatment group experiencing an adverse event
- PT will be alphabetically reported

The following tables will be reported:

- TEAE
  - Any TEAE by SOC
  - Any TEAE by SOC and PT\*
  - Any TEAE by PT
  - Any TEAE by PT by NCI CTCAE Grade
  - Any TEAE by PT by cycle

- Any TEAE by PT by NCI CTCAE Grade by cycle
- Related TEAE
  - Any TEAE by SOC and PT\*
  - Any TEAE by PT
  - Any TEAE by PT by NCI CTCAE Grade
- TEAE NCI CTCAE Grade 3 or higher
  - Any TEAE by SOC and PT
  - Any TEAE by PT
- Related TEAE NCI CTCAE Grade 3 or higher
  - Any TEAE by SOC and PT
  - Any TEAE by PT
- SAE TEAEs only
  - Any SAE by SOC and PT\*
  - Any SAE by PT
- TEAE Various
  - Any TEAE Resulting in Dose Reduction
  - Any TEAE Resulting in Treatment Discontinuation
  - Any TEAE Resulting in Death

In the AE preferred term summary tables, a patient having multiple events within a System Organ Class is counted only once for that SOC. Similarly, a patient having multiple events under a preferred term is counted only once for that PT. Listings will be provided for all adverse event data.

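### SAP 3.6.1, read literally, leaves out on-drug recurrences of resolved events that SAP 5.6.2 would count, and nothing says which rule governs

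*SAP*

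**What the plan says.** SAP 3.6.1 gives two routes to treatment-emergent status. The first is for events that begin on treatment, up to and including day 30 after the final dose, with the added condition "and was not observed prior to start of treatment". The second is: "The event was observed prior to the start of treatment but increased in NCI CTCAE v4 grade during study treatment". The section then sends treatment-emergent events to the adverse event page of the eCRF and pre-treatment events to medical history.

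SAP 5.6.2 defines the term again, "based on the event onset date relative to first dose of study drug in the study". It has no condition on earlier observation, no route for worsening and no reference to 3.6.1. It counts events with a missing onset date and excludes those starting 30 or more days after the last dose. It also fixes what is tabulated: "Summary tables will include treatment-emergent AEs, unless specified otherwise".

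Protocol 10.5.4 has two wordings. One requires that an event occurring after first dose "was not present prior to study drug administration or worsened in severity after study drug administration". The other covers "adverse events that occur or worsen in severity following the first dose of seribantumab, or fulvestrant". Collection runs to the end of treatment visit.

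Protocol 10 states: "The SAP may modify the plans outlined in the protocol". Protocol 9.2 covers everyone between consent and eligibility determination, and heregulin-positive patients after that. Its instruction is that "all adverse events, whether serious or not, will be described in the source documents and the adverse event page of the case report form".

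**The concern.** The two SAP sections can classify the same record differently. The main case is a toxicity of earlier therapy that has resolved by first dose and comes back on study drug at the same or a lower grade. It has been observed before, so it fails the first route in 3.6.1. Its grade has not risen, so it fails the second. By onset date it is plainly on-treatment, and 5.6.2 would count it.

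This history is plausible here. Protocol 4.1 requires recovery from clinically significant effects of prior antineoplastic therapy, and protocol 4.2 allows standard systemic therapy to end as little as 14 days before first dose. Describing safety is a stated secondary objective. Two programmers following the same SAP could therefore produce different adverse event tables, and the choice between definitions could be made after the data are seen.

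**Working it through.** No stated sample size, power or alpha depends on this point, so there is no figure of the plan to reproduce. The check applies each SAP rule literally to the same event histories.

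| Event history | SAP 3.6.1 | SAP 5.6.2 alone |
|---|---|---|
| New onset on treatment | counted | counted |
| Resolved before first dose, recurs at a higher grade | counted | counted |
| Resolved before first dose, recurs at the same or a lower grade | **not counted** | **counted** |
| Ongoing at first dose, worsens, entered with a post-dose onset date | counted | counted |
| Ongoing at first dose, worsens, pre-dose onset date kept | **counted** | **not counted** |
| New onset 29 days after last dose | counted | counted |
| New onset exactly 30 days after last dose | **counted** | **not counted** |
| New onset 31 days after last dose | not counted | not counted |

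The rules disagree in three rows. The recurrence row needs no assumption about data entry. The worsening row needs two conditions: that 5.6.2 is used without 3.6.1, and that the record keeps its pre-dose onset date. The day-30 row is a boundary difference that any single definition must also settle.

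**Does anything rank the rules?** Protocol 10 ranks the SAP against the protocol, not one SAP section against another. Both wordings in protocol 10.5.4 keep worsening, which supports 3.6.1 there. On recurrence they pull apart: the first can be read to exclude an event that was present earlier and resolved, while the second includes anything that occurs after first dose.

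**Tables exposed.** SAP 5.6.2 lists 6 (TEAE) + 3 (related) + 2 (grade 3 or higher) + 2 (related, grade 3 or higher) + 2 (serious) + 3 (various) = 18 tables. In the recurrence case:
- The table of events resulting in death cannot differ, because Grade 5 always exceeds the earlier grade and so meets the grade-increase route.
- The 4 grade 3 or higher tables can differ only if the earlier episode was also grade 3 or higher.
- The other 18 − 1 − 4 = 13 can differ with no condition on the earlier grade.

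**Weight of one patient.** The denominator is dosed patients (SAP 2.2). Assuming everyone randomized is dosed:
- Protocol 10.2: 80 patients at 1:1 gives 80/2 = 40 per arm, and 1/40 = 2.5 percentage points.
- SAP 5.1: 286 patients at 2:1 gives 286 × 2/3 = 190.7 and 286 × 1/3 = 95.3, so 1/190.7 = 0.52 points (seribantumab) and 1/95.3 = 1.05 points (control).

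These are upper limits per affected patient. SAP 5.6.2 counts a patient once per preferred term and once per System Organ Class, so a cell changes only if she has no other qualifying event in it.

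**Is there a pre-dose grade to compare with?** Protocol 9.2 puts events after consent on the adverse event page, and protocol 9.4.1 grades adverse events. SAP 3.6.1 puts pre-treatment events in medical history, for which protocol 7.1 lists no grade. The two instructions differ and the CRF was not seen, so a baseline grade for ongoing conditions is not assured.

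**The case against.** The strongest reply is that 3.6.1 is the definition and the sentence in 5.6.2 is loose shorthand for it. Section 3.6.1 carries the term as its heading and sets out criteria. The sentence in 5.6.2 is garbled, does not say before or after first dose, and sits among missing-data conventions. That reading is possible. But 5.6.2 does not say so, and it adds a missing-onset rule and a different closing day, so it can also be applied as a second definition. If 3.6.1 does govern, the recurrence is simply left out.

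It may also be said that 3.6.1 does not define an event: if each episode is its own event, a recurrence occurs for the first time on drug. On that reading the condition about earlier observation would do no work, because an episode starting on drug could never have been seen before. Excluding same-grade recurrences could instead be a deliberate baseline adjustment, but then 5.6.2 should not count them.

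On worsening the reply largely succeeds. A reader might infer that the two rules fail equally in both directions. The documents do not support that. SAP 3.6.1 and both wordings in protocol 10.5.4 count worsening, silence in 5.6.2 does not repeal them, and protocol 9.2 requires worsened events to be reported. No text says that such a record keeps its old onset date.

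Finally, the SAP names protocol seribantumab-02-03-10, a phase 3 trial, not MM-121-02-02-10. That is a larger matter, but the inconsistency lies within the SAP and would survive a reissue that copied these sections.

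**Conclusion.** The point holds for recurrence: literal 3.6.1 excludes, and 5.6.2 counts, an event that resolved before first dose and recurs on drug at the same or a lower grade. Nothing in either document settles which applies. Loss of worsening is a conditional, secondary point.

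Severity is minor. How many patients would be affected cannot be estimated from the documents, and no rate is assumed. The figures of 2.5, 0.52 and 1.05 points are the weight of a single patient if all randomized patients are dosed, not an expected shift. A reader might infer that the safety comparison is biased between arms or that toxicity is hidden. The documents do not show that: the same rule applies to both blinded arms, the size and direction of any difference are unknown, and the listings cover all adverse events. No tested endpoint is affected.

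**What to change.** Put one definition in SAP 3.6.1. Have 5.6.2 refer to it in place of its own onset-date and day-30 sentences, and align protocol 10.5.4. Suggested wording:

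> An AE is treatment-emergent if its onset is on or after first dose and on or before 30 days after the last dose, including recurrence of an event that had resolved before first dose, or if it was ongoing at first dose and worsened in CTCAE grade within that window.

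Two recording rules should go with it:
- State that a worsened event is entered on the adverse event page with the date of worsening.
- Reconcile SAP 3.6.1 with protocol 9.2 on where pre-dose events are recorded, so that every condition ongoing at first dose has a pre-dose grade.

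If the SAP is reissued for this protocol, carry the single definition into it. The cost is wording in two documents, plus a first-dose grade for ongoing conditions held only as medical history if the CRF does not already collect one. The downside is slightly higher treatment-emergent rates in both arms than under 3.6.1 as written. The change should be made before database lock.

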## 6.3.1. RNA-ISH Heregulin Testing

All patients must submit a tissue sample for RNA-ISH testing of heregulin levels as soon as possible following signing the informed consent form, as this will determine patient eligibility for treatment randomization and subsequent screening procedures. The HRG RNA-ISH assay can be used to measure mRNA expression on tissue slides obtained from formalin-fixed paraffin embedded archived blocks, core biopsies or fine needle aspirates; therefore, any of these methods of collection is acceptable for testing.

If archive tissue is being used for eligibility testing, the most recent sample available should be submitted. Heregulin testing can be performed on tissue obtained at the following times:

- At the time of initial diagnosis
- At the time of metastatic diagnosis
- or on tissue obtained from a fresh tumor biopsy.

If collection of fresh tissue is required in order to provide adequate tissue for testing, attempts should be made to acquire tissue from a tumor in a non-significant risk location, as determined by the investigator. As a general guideline, if the selected procedural location of the core needle biopsy or FNA has an established serious complication rate of >2% at the institution completing the procedure, this is considered a high risk procedure and should be avoided. Primary tumor samples and samples obtained from metastatic sites are both acceptable.

Preparation of samples for HRG testing should be conducted in accordance with the laboratory manual. Specific procedures for the collection and processing of bone biopsies are provided in the manual.

Samples will be processed and analyzed at a central facility where they are scored by a pathologist as specified in the lab manual with a turnaround time of no longer than 7 days from date of receipt by the central lab. Any patient who scores positive (a score of  $\geq 1+$ ) for HRG mRNA will be eligible for the study and should continue with screening procedures.

<sup>2 Any serious adverse events considered by the Investigator to be directly related to screening procedures (i.e. related to screening biopsy) should be collected and reported from the time of informed consent up to receipt of HRG results.

<sup>3 Minimal medical history will be collected from all HRG negative patients.

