# 8.7.2. Tumor Biopsy

Prior to receiving the first dose of study drug, all HRG positive patients should provide one fresh tumor biopsy for research purposes. This biopsy will be used to confirm HRG status, and samples will be used to conduct exploratory studies to further characterize and correlate possible biomarkers that may help to predict or evaluate response to seribantumab. Patients who undergo a fresh tumor sample for eligibility testing do not need to provide an additional sample.

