#### 9.3. Reporting Serious Adverse Events

Serious adverse events (SAE) will not be reported for patients who only sign the pre-screening consent form or for heregulin negative patients unless the serious event is directly related to a study procedure (i.e. tumor biopsy). Serious adverse event reporting will begin in conjunction

with the date of signing the main study informed consent. Any SAEs occurring prior to study drug administration that the investigator believes may have been caused by a protocol procedure must be reported immediately to the Sponsor or its designee and recorded on the case report form. Serious adverse event reporting for HRG negative patients is not required unless the event is directly related to a procedure performed for this trial.

All fatal or life-threatening adverse events must be immediately reported to the Sponsor or CRO's medical team by telephone or e-mail. Within 24 hours of the event, the Serious Adverse Event Form must be faxed to the Drug Safety Manager whether full information regarding the event is known or not. Additional follow-up by the investigator will be required if complete information is not known. De-identified source documentation of all examinations, diagnostic procedures, etc. which were completed with respect to the event should be included with the SAE form. Care should be taken to ensure that the patient's identity is protected and the patient's identifiers (as assigned at the time of study enrollment) are properly mentioned on any copy of source document provided to the Sponsor. For laboratory results, include the laboratory normal ranges.

In case of accidental or intentional overdose of study drug (seribantumab or fulvestrant), even if asymptomatic or not fulfilling a seriousness criterion, the overdose is to be reported to the Sponsor or Medical Monitor immediately (within 1 working day) using the AE and SAE forms. Overdose of study drug will be defined as  $\geq$ 3300 mg of seribantumab, or  $\geq$ 133% of planned dose of fulvestrant.

All other serious adverse events must be reported to the Drug Safety Manager within 24 hours by phone, e-mail or fax. Details are outlined in the study procedure manuals. The Serious Adverse Event Form must also be faxed to the Drug Safety Manager within 24 hours of the event whether full information regarding the event is known or not. Additional follow-up by the investigator will be required if complete information is not known.

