## 5.6 Safety Analysis

All safety analysis will be performed using the safety population.

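### The SAP sends events before first dose to medical history, against the protocol's adverse-event rules, and no planned SAP summary table is designed to show biopsy complications before dosing or in screen failures

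*SAP*

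**What the plan says.** **Where pre-dose events are recorded.** SAP 3.6.1 puts treatment-emergent events on the AE page and says that "those events occurring pre-treatment will be captured on medical history". SAP 5.4.2 then codes medical history and summarizes it by system organ class and preferred term, alongside demographics and cancer diagnosis. Protocol 9.2 says otherwise: "For all patients between informed consent and eligibility determination and for heregulin positive patients during their time on study, all adverse events", serious or not, go into the source documents and onto the AE page. Protocol 7.2 starts AE reporting at the main consent. For patients who have signed only the biomarker consent, it keeps just the events directly related to a study procedure, with the biopsy for heregulin testing as its example. Protocol 9.3 requires pre-dose SAEs that a protocol procedure may have caused to be reported at once and entered on the CRF.

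**What is tabulated.** SAP 5.6: "All safety analysis will be performed using the safety population". SAP 2.2 defines that population as patients with at least one dose. SAP 5.6.2: "Summary tables will include treatment-emergent AEs, unless specified otherwise". None of the tables it lists is specified otherwise, and the SAE block is headed "SAE TEAEs only". SAP 5.6.2 and Protocol 10.5.4 both also promise listings of all AE data.

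**The procedure.** Protocol 8.7.2: "Prior to receiving the first dose of study drug, all HRG positive patients should provide one fresh tumor biopsy for research purposes", unless a fresh sample was already taken for eligibility. Protocol 3.1 and 6.3.1 also provide for a fresh biopsy for the HRG test when existing tissue is inadequate, so some screen failures will be biopsied too.

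**HRG-negative patients.** Protocol 9.3: "Serious adverse event reporting for HRG negative patients is not required unless the event is directly related to a procedure performed for this trial". Footnote 2 to the schedule in Protocol 6.2 (its text is printed at the end of 6.3.1 in the copy reviewed) says that SAEs related to screening procedures "should be collected and reported from the time of informed consent up to receipt of HRG results".

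**The concern.** The fresh biopsy is a risk that the trial itself creates. It is asked of HRG-positive patients before any study drug, and Protocol 10.3 makes HRG confirmation on fresh tissue a condition of the primary Per Protocol population. Some patients who never receive study drug are biopsied as well. Protocol 3.1 recognizes that the procedure can have serious complications.

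If the SAP sentence is followed, a complication of that biopsy is entered as history and later appears among pre-existing conditions. If the protocol is followed, it is entered as an AE, but the SAP has no table designed to hold it. In both cases the final report could not readily give a number of biopsy complications over a number of patients biopsied. The accuracy of harm reporting is at stake. The efficacy analysis is not affected.

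**Working it through.** The plan states no figure on this point, so there is none to reproduce. The check is to follow three illustrative events through both documents.

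| Event | Recorded under the protocol | Recorded under SAP 3.6.1 | SAP summary table |
|---|---|---|---|
| A. Randomized patient, non-serious complication of the research biopsy, resolved before first dose | AE page (9.2) | Medical history | No AE table; appears in the baseline history summary (5.4.2) if the SAP is followed |
| B. As A, but serious | Immediate report to the sponsor, and CRF (9.3) | Medical history | None; SAE tables are treatment-emergent only (5.6.2) |
| C. HRG-negative patient biopsied for testing, complication becomes serious after the HRG result | Reportable under 9.3; outside the window in the 6.2 footnote | Medical history | None; never in the safety population (2.2) |

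What follows from the table:

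1. **Recording conflict.** In A and B the protocol and SAP 3.6.1 name different forms for the same event.
2. **Effect on listings.** The listings cover AE data. An event held only as medical history is not AE data, so the SAP routing would also take A out of the AE listing.
3. **Table gap.** Event A is in no AE table even when it is recorded as the protocol asks, because its onset precedes treatment.
4. **Exceptions.** A pre-dose event that rises in grade on treatment becomes treatment-emergent (SAP 3.6.1), and an event with a missing onset date is counted as treatment-emergent (SAP 5.6.2). Event B could also enter the SAE tabulation in Protocol 10.5.4, which is not worded as treatment-emergent, provided the patient is later dosed.
5. **Collection window.** In C, Protocol 9.3 sets no end for procedure-related SAEs. The 6.2 footnote ends collection at the HRG result, which Protocol 4.3.2 expects within 7 days of sample receipt at the central laboratory.

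**Scale (illustrative).** Inputs: 80 randomized and about 200 screened (Protocol 10.2); one fresh biopsy per randomized patient (assumed from 8.7.2); serious-complication rate p of 0.5% to 2% (assumed; 2% is the institutional level in Protocol 3.1 above which a biopsy location is to be avoided).

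Expected events = n × p; chance of at least one = 1 − (1 − p)^n.

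- n = 80, p = 0.005: 80 × 0.005 = 0.4; 1 − 0.995^80 = 0.33.
- n = 80, p = 0.02: 80 × 0.02 = 1.6; 1 − 0.98^80 = 0.80.

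A further 200 − 80 = 120 patients are screened but not randomized. The documents do not say how many of them would have a fresh biopsy. If none did, nothing is added. If all 120 did, the addition is 120 × 0.005 = 0.6 to 120 × 0.02 = 2.4 expected serious events, all outside the safety population.

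**The case against.** The strongest defense is that the protocol already treats these events as harms. It records AEs from consent, sends serious procedure-related events to the sponsor at once, and names the biopsy as the reason to keep reporting for patients who signed only the biomarker consent. Both documents list all AE data. The safety objective is the profile of seribantumab with fulvestrant, and treatment-emergent tables in dosed patients suit that aim. Biopsies before dosing fall on both arms and do not bias the comparison. All of this stands, and it limits the point to a recording conflict and a missing summary.

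A reader might infer that biopsy harm would never be counted, or that the report must show none. The documents do not support that, because of the sponsor reporting, the listings and the exceptions in the working.

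A reader might also infer that the DMC is left unable to check a 2% limit. That does not hold either. The 2% figure is an institution's established rate and guides the choice of biopsy site; it is not a trial-level monitoring threshold. DMC review follows a charter that is not among the documents.

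Protocol 9.2 might seem to contradict 7.2 on which events are recorded before eligibility is known. If the consent in 9.2 means the main consent, the two agree, so this is unclear wording at most. Protocol 9.2 also has a sentence that ties the duty to report new or worsening events to the period after first administration. Read alone, it could favor the SAP. But the sentence before it puts earlier events on the AE page, and 7.2 starts at main consent.

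Finally, SAP section 1 names protocol seribantumab-02-03-10 and SAP 1.2 describes a phase 3 trial with exemestane or fulvestrant, so its eCRF sentence may not describe this trial's CRF. That is a reason to check the CRF. It does not remove the conflict in the SAP supplied.

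**Conclusion.** The point holds in limited form. SAP 3.6.1 contradicts Protocol 7.2, 9.2 and 9.3 on where events before first dose are recorded. No planned SAP summary table is designed to show procedure-related events before dosing or in screen failures. If the SAP routing were followed, such events would also drop out of the AE listing and be read as baseline history. The cut-off at the HRG result in the 6.2 footnote is a separate, smaller inconsistency with Protocol 9.3.

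The numbers are small: 0.4 to 1.6 expected serious events among 80 biopsies, with a 33% to 80% chance of at least one, plus an unknown number among screen failures. These figures rest on an assumed complication rate and one biopsy per randomized patient. The upper end applies the avoidance level to every biopsy, so it is close to a ceiling. The contradiction itself rests on the text alone. It should be corrected because the remedy is cheap and uses data that the protocol already requires.

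**What to change.** 1. In SAP 3.6.1, replace the medical-history sentence with a statement that events after consent go on the AE page as Protocol 7.2, 9.2 and 9.3 require. Reserve medical history for conditions present before consent. Check the new wording against this trial's CRF, since the SAP is labelled for another protocol.
2. In SAP 5.6.2, add one table, or a dedicated listing with a denominator, of biopsy-related AEs and SAEs with onset before first dose. The denominator is all patients who had a study biopsy, with randomized patients and screen failures shown separately. For screen failures, limit it to the procedure-related events that the protocol already requires.
3. Reconcile footnote 2 of the Protocol 6.2 schedule with Protocol 9.3, so that both give the same end of collection for procedure-related SAEs in HRG-negative patients.
4. While editing, state in Protocol 9.2 which consent form starts the recording period.

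**Cost.** Items 1 and 2 need SAP wording, one output and a reliable record of who was biopsied. Items 3 and 4 are protocol wording. There is no new procedure. If the sponsor settles item 3 by dropping the cut-off, sites may need some contact with HRG-negative patients after the result. The 6.2 schedule, which has only a screening visit, does not now provide for that.
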